### **1.1. Experience with the use of convalescent plasma against coronavirus diseases**

In the 21st century, there were two other epidemics with coronaviruses that were associated with high mortality, SARS1 in 2003 and MERS in 2012. In both outbreaks, the high mortality and absence of effective therapies led to the use of convalescent plasma. The largest study involved the treatment of 80 patients in Hong Kong with SARS (Cheng et al., 2005). Patients treated before day 14 had improved prognosis defined by discharge from hospital before day 22, consistent with the notion that earlier administration is more likely to be effective. In addition, those who were PCR positive and seronegative for coronavirus at the time of therapy had improved prognosis. There is also some anecdotal information on the use of convalescent plasma in seriously ill individuals. Three patients with SARS in Taiwan were treated with 500 ml of convalescent plasma, resulting in a reduction in plasma virus titer and each survived (Yeh et al., 2005). Three patients with MERS in South Korea were treated with convalescent plasma, but only two of the recipients had neutralizing antibody in their plasma (Ko et al., 2018). The latter study highlights a challenge in using convalescent plasma, namely, that some who recover from viral disease may not have high titers of neutralizing antibody (Arabi et al., 2016). Consistent with this point, an analysis of 99 samples of convalescent sera from patients with MERS showed that 87 had neutralizing antibody with a geometric mean titer of 1:61. This suggests that antibody declines with time and/or that few patients make high titer responses.

It is also possible that other types of non-neutralizing antibodies are made that contribute to protection and recovery as described for other viral diseases (Gunn et al., 2018; van Erp, Luytjes, Ferwerda, & van Kasteren, 2019). There are reports that convalescent plasma was used for therapy of patients with COVID-19 in China during the current outbreak (Xinhua, 2020). Although few details are available from the Chinese experience and published studies involved small numbers of patients, the available information suggests that convalescent plasma administration reduces viral load and was safe.

Convalescent plasma, compared to normal control plasma, was recently shown to confer lower mortality in New York City and Brazil among adults hospitalized with

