### 2.3.5 Stratified Randomization

1. Subjects enrolled in the study will be stratified and randomized using an interactive web- based system

 Assessment evaluates whether subject has shifted from “no clinical or laboratory evidence of COVID-19 infection to any of the composite outcomes of disease severity

[figure not shown]
 Comprehensive metabolic panel

 Nasal swab

 Includes sequencing for viral variants

 10 % sample of the nasal swabs

2. Subjects will be stratified by steroid administration (prior oral or IV steroids within prior 2 weeks at time of enrollment or prior inhaled steroids within prior 24 hours at time of enrollment) and by vaccination status (prior COVID-19 vaccine at time of enrollment) and then randomized in a 2:1 ratio to either CP or albumin 5%

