## 3 STATISTICAL CONSIDERATIONS

### 3.1 Design Overview

This is a double-blinded, randomized phase 2 trial to evaluate the efficacy and safety of human SARS-CoV-2 immune plasma in individuals who are close contacts to person with COVID-19 within 7 days according to the CDC definition. This will also serve as an internal pilot in the seamless phase 2/3 study.

Eligible participants will be randomized to receive high-titer anti-SARS-CoV-2 immune plasma or control (albumin 5%) in a 2:1 ratio. We plan to enroll a total of 150 participants, with a maximum of 100 receiving the plasma and 50 receiving the control.

Each participant will be followed for 28 days after randomization and treatment, and will be tested and evaluated at baseline and on Days 3, 7, 14, 28 using a seven-category severity scale:

1. Not hospitalized, negative PCR for SARS-CoV-2
2. Not hospitalized, positive PCR for SARS-CoV-2 without symptom
3. Not hospitalized, positive PCR for SARS-CoV-2 with symptoms
4. Non-ICU hospitalization, not requiring supplemental oxygen
5. Non-ICU hospitalization, requiring supplemental oxygen
6. Requiring mechanical ventilation and/or in ICU
7. Death

The primary study endpoint is the rating on Day 28, or last rating evaluated. We will also consider time to various dichotomizations on this scale as secondary

outcomes, including time to death, time to requiring critical care, and time to requiring hospitalization

Other endpoints include:

- Anti-SAR-CoV-2 titers (Days 3, 7, 14, 28, 90 in addition to baseline)
- SAR-CoV-2 PCR positivity (Days 0, 3, 7, 14, 28 in addition to baseline)
- SAR-CoV-2 RNA (Days 0, 3, 7, 14, 28 in addition to baseline)

Exploratory objective:

- To assess the correlation between SARS-CoV-2 PCR positivity from nasal swab specimens, based on RT PCR, and detection of viable SARS-CoV-2 from nasal swab specimens based on viral culture assays

Serious adverse events, and grades  $\geq 3$  adverse events will be monitored during the study period.

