## 3.2 Statistical Analysis

Primary Analysis and go/no-go decision: The severity scale of the two groups will be compared using stratified, Mann Whitney test. Specifically, a one-sided  $P < 0.15$  favoring the immune plasma arm will constitute a “go decision” in this phase 2 trial, suggesting evidence of promise for further investigation in an expanded Phase 3 study. The results in this trial will then be used to plan the Phase 3 sample size, with possibility that the data in this Phase 2 trial will be included in the final analysis using adjusted  $P$  values. Details of sample size re-estimation and adjusted analysis, as well as the final statistical analysis plan, will be determined before unblinding the study data.

This analysis will be intent-to-treat. Given the short study duration and the nature of the treatment, however, we anticipate minimal non-compliance and loss to follow-up.

Subgroup Analysis: If the stratified analysis reaches the go decision, with  $P < 0.15$ , we will explore the treatment effect within each stratum using Mann Whitney test.

Secondary Analyses: All secondary efficacy analyses will be intent-to-treat. Time-to-event variables (e.g. time to death) will be analyzed using Cox proportional hazard model. Longitudinal data collected over multiple days (e.g., PCR positivity) will be analyzed using generalized linear mixed models. Treatment effects on these variables will be estimated with 95% confidence intervals.

Safety Analyses: Serious adverse events will be summarized by grades and types using proportions and 95% confidence intervals for the two study arms, and the two arms will be compared using Fisher's exact test.

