### 3.3 Power Consideration

Assuming a shift odds ratio of 2 under a proportional odds model on the severity rating scale, with a sample size of 150, the study will have 74% to 80% power of reaching the go decision in the scenarios we considered. The actual power will depend the distribution of the severity scale in the control arm. Table 2 gives the power of the two extreme scenarios: Scenario 1 describes scenario with higher rates for more severe outcomes, and Scenario 2 with majority of participants remaining or becoming PCR negative; the outcome distributions are identical between the two strata in these scenarios. We have evaluated the power for in-between scenarios and scenarios where non-infected and infected strata are different; the power is within the range 74% and 80% in all scenarios we have considered.

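### Subgroup effects are explored only after a go and only by separate tests in each stratum, which do not show whether the effect differs between strata (minor)

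*Combined protocol and SAP*

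**What the plan says.** Section 3.2 sets the primary analysis: "The severity scale of the two groups will be compared using stratified, Mann Whitney test". A one-sided P below 0.15 "favoring the immune plasma arm will constitute a" go decision. The subgroup paragraph is conditional on that result: "If the stratified analysis reaches the go decision", then "we will explore the treatment effect within each stratum using Mann Whitney test". It gives no interaction test, no contrast between strata, no subgroup effect measure or interval, and no subgroup analysis after a no-go. The 95% intervals promised in the same section belong to the secondary variables.

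Section 2.3.5 defines the randomization strata: "Subjects will be stratified by steroid administration" and by prior COVID-19 vaccination, which crossed give four cells. Section 3.3, however, speaks of two strata and of infected versus non-infected strata. So it is not clear what each stratum in Section 3.2 refers to.

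Anti-SARS-CoV-2 titers are measured at screening, before infusion (Schedule of Events; Sections 3.1 and 4.2). No analysis by baseline serostatus is planned, although Section 1.1 reports from an earlier SARS series that "those who were PCR positive and seronegative for coronavirus at the time of therapy had improved prognosis".

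**The concern.** A test in one stratum asks whether the effect there differs from zero. Two such tests, one passing and one failing, do not show that the effects differ from each other; with small strata that pattern is expected even when the effect is the same everywhere. Here the tests are also read only after the overall result has come out favourable, which raises the chance that some stratum looks positive. If instead the benefit is confined to part of the population and the overall test misses, the plan provides no stratum estimate at all.

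What is at stake is interpretation. Section 3.2 says that the results will be used to plan the Phase 3 sample size, and Section 3.1 calls the trial an internal pilot for a seamless phase 2/3 study. Mixed stratum results could be carried into that planning as if they were evidence of heterogeneity.

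**Working it through.** **Inputs from the documents.** Sample size and split, Section 3.1: "We plan to enroll a total of 150 participants, with a maximum of 100 receiving the plasma and 50 receiving the control". Effect, Section 3.3: "Assuming a shift odds ratio of 2 under a proportional odds model on the severity rating scale, with a sample size of 150". Control-arm distributions: the two control columns of Table 2. Go threshold: one-sided 0.15.

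**Assumptions.** Stratum sizes are not in the documents, so equal and uneven layouts were tried. The stratified test is read as van Elteren's: Z = Σ w(W − E) / √(Σ w²V), with w = 1/(N + 1) in each stratum and tie-corrected V. A go is Z > z(0.85). Loss to follow-up is not modelled.

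**Step 1. Reproduce the stated power.** Section 3.3 gives 74% (Scenario 1) and 80% (Scenario 2). Simulation with the Table 2 rates gives 74.2% and 81.1% unstratified, 74.0% and 80.9% with two strata, and 74.4% and 80.7% with four. The set-up therefore matches the sponsor's. A two-sided 0.15 reading gives only 60–69%.

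**Step 2. Power inside a stratum** (one-sided 0.15, odds ratio 2):

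| Stratum size | Scenario 1 | Scenario 2 |
|---|---|---|
| 75 | 56.5% | 62.1% |
| 45 | 46.6% | 50.8% |
| 38 | 43.8% | 47.4% |
| 15 | 33.9% | 34.5% |

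**Step 3. Same odds ratio of 2 in two strata of 75, after a go.** If both strata pass, the overall test passes too, so P(both pass | go) ≈ (within-stratum power)² / P(go).
- Scenario 1: 0.565² / 0.743 = 0.319 / 0.743 = 0.43 (simulated 0.432).
- Scenario 2: 0.621² / 0.810 = 0.386 / 0.810 = 0.48 (simulated 0.483).

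In nearly all the remaining go trials one stratum passes and the other fails: 53.7% and 49.1%, or about 49–54%. With strata of 105 and 45 the figure is 53–57%; with 120 and 30 it is 58–60%. With four strata the results are mixed in about 93–94%.

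**Step 4. An interaction contrast on the same data.** For two equal strata take D = (z₁ − z₂)/√2 and flag |D| > z(0.95), which is two-sided 0.10. The overall statistic is close to (z₁ + z₂)/√2, which is nearly independent of D, so selecting on a go hardly disturbs it. Simulated flag rate after a go: 11.5% and 10.9%. Over all trials: 11.3% and 10.9%.

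**Step 5. No effect anywhere, four strata.** About 15% of trials are a false go. Among those, 58–61% show at least one stratum at one-sided P<0.05, and repeat runs differ by a point or two. As a share of all null trials: 0.15 × 0.58 = 0.087 to 0.15 × 0.61 = 0.092, about 9%.

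**Step 6. Benefit in one of two equal strata, none in the other.** The trial is a no-go in 54–58% (odds ratio 2) and 38–44% (odds ratio 3); across runs the range is 38–59%. In 38–65% of these no-go trials the responsive stratum alone would have one-sided P<0.15. The comparator is the null case, where a given stratum of two does so in about 8% of no-go trials.

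**Step 7. Precision of the remedy.** With two halves of 75, the standard error of the log ratio of odds ratios is 0.74–0.81. Then 1.96 × 0.74 = 1.45 and 1.96 × 0.81 = 1.59, so the 95% limits are the estimate divided and multiplied by about 4.3 to 4.9. Power of the contrast at two-sided 0.10 is about 23–44% for an odds ratio of 2 to 3 against 1.

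**The case against.** The strongest reply is that the analysis is labelled exploratory, that gating subgroups on the overall result is a recognised guard against rescuing a failed trial, and that interaction estimates here will be too imprecise to settle anything.

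Much of this stands. With no effect and four strata, 19–20% of trials would show some stratum at one-sided P<0.05 without a gate; the gate brings that to about 9%. So the gate itself is not an error, and showing estimates after a no-go is a preference that can be debated. Imprecision is real too (step 7): an interaction estimate would usually miss a moderate difference. But an interval shows how little is known, whereas a pair of discordant P values hides it.

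Four stronger readings are tempting, and the documents do not support them.
- A reader might infer that the stratum results decide whom Phase 3 enrols. Section 3.2 mentions only its sample size.
- A reader might infer that a no-go is the likely outcome whenever one stratum fails to respond. At an odds ratio of 3 in half the patients it is 38–44%, and with odds ratio 2 in 70% of patients it is 39–45%. It passes one half only when the effect is weak or the responsive stratum small.
- A reader might take serostatus as an established effect modifier. Section 1.1 describes prognosis among treated SARS patients and reports no untreated comparison. That makes modification plausible, not shown. Vaccination, a partial proxy, is already a stratum.
- A reader might conclude that a stratum effect can never be looked for. Section 3.2 leaves the final analysis plan to be settled before unblinding, so it could still be added.

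**Conclusion.** The point holds as a minor one. The planned separate tests do not answer the question that a subgroup analysis asks, and under equal effects they give discordant answers in about half of go trials (49–54% with two strata of 75), against about 11% for a direct contrast. The two figures use different cut-offs, one-sided 0.15 and two-sided 0.10, so they compare what a reader would see under each approach, not two tests at one level. After a no-go, which occurs in 38–59% of trials when an odds ratio of 2 to 3 is confined to one of two equal strata, no stratum estimate is planned.

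These sizes rest on assumed stratum sizes, the Table 2 control columns, proportional odds, the van Elteren reading and no dropout. The four-strata figures also depend on taking the strata from Section 2.3.5, which Section 3.3 does not match. The primary test, its error rate and the go decision are unaffected.

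**What to change.** In the final analysis plan, before unblinding:

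1. Replace the within-stratum Mann-Whitney P values by proportional-odds models (the model that Section 3.3 already assumes) with a treatment-by-factor term, one factor at a time, for vaccination, steroid use and baseline serostatus from the screening sample. Fix the definition of seropositive in advance.
2. Report the odds ratio at each factor level and the ratio of odds ratios, all with confidence intervals and labelled exploratory.
3. Preferably show the same table descriptively after a no-go, stating that it cannot overturn the decision.
4. Define each stratum, and reconcile Section 2.3.5 (steroid use and vaccination) with Section 3.3 (two strata; infected and non-infected).

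The cost is analysis-plan wording and three models on data already being collected. The downside is wide intervals, and small factor levels will still vary in sign by chance, so the text should say that a non-significant interaction is not evidence of a uniform effect.

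### Time to death is assigned to a Cox model, but Table 2 implies so few deaths that a finite hazard ratio and two-sided interval may well not exist

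*Combined protocol and SAP*

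**What the plan says.** Section 3.1 makes times to several cut-points of the seven-category scale secondary outcomes, "including time to death, time to requiring critical care, and time to requiring hospitalization". Section 3.2, Secondary Analyses, fixes the method: "Time-to-event variables (e.g. time to death) will be analyzed using Cox proportional hazard model". It adds: "Treatment effects on these variables will be estimated with 95% confidence intervals".

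On size, Section 3.1 states: "We plan to enroll a total of 150 participants, with a maximum of 100 receiving the plasma and 50 receiving the control". On event rates, Section 3.3 says "Table 2 gives the power of the two extreme scenarios". Table 2 puts death at 5% (control) and 2% (plasma) in Scenario 1, and at 2% and 1% in Scenario 2.

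Sections 3.1 to 3.3 give no expected number of deaths, no minimum event count for fitting the model, and no alternative if an arm has no events. Section 3.2 does say that the final statistical analysis plan will be settled before the data are unblinded.

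**The concern.** Death is the one outcome that the plan names as its example for the Cox model, and it is the rarest category in Table 2 apart from those set at 0% or tied with it. When all deaths fall in one arm, the partial likelihood is monotone: the estimated hazard ratio runs to zero or infinity and no finite two-sided interval exists. When nobody dies, there is nothing to estimate.

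The stake is a promised estimate that may not be available, and a substitute chosen after seeing which arm is empty. Two things in the protocol give this some weight. Section 1.1 cites a randomised plasma trial in severe disease in which mortality was lower although the Day 28 ordinal status did not differ, so mortality and the ordinal scale can tell different stories. Section 3.2 also says that these data will be used to plan Phase 3 and may enter its final analysis.

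**Working it through.** **Inputs.** Arm sizes are 50 control and 100 plasma (Section 3.1). Rates come from Table 2, and the odds ratio of 2 from Section 3.3. Losses are taken as zero, because Section 3.2 expects them to be minimal and gives no figure. Death is absorbing, so the Day 28 proportion in category 7 is also the cumulative proportion dead by Day 28.

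**The plan's own figure first.** The documents state power only for the primary test: 74% and 80%. Simulating 40,000 trials with a stratified Mann-Whitney test (50 vs 100, one-sided 0.15, one or two equal strata) gives 73.8–74.0% and 81.0–81.1% at the printed rates, and 75.1–75.2% and 80.4% at an exact odds ratio of 2. The design is therefore being read as intended.

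**Expected deaths** = 50·pC + 100·pT.
- Scenario 1: 50 × 0.05 + 100 × 0.02 = 2.5 + 2.0 = 4.5.
- Scenario 2: 50 × 0.02 + 100 × 0.01 = 1.0 + 1.0 = 2.0.

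**Chance that at least one arm has no deaths** = 1 − [1 − (1 − pC)^50] × [1 − (1 − pT)^100].
- Scenario 1: 0.95^50 = 0.077 and 0.98^100 = 0.133, so 1 − 0.923 × 0.867 = 19.9%.
- Scenario 2: 0.98^50 = 0.364 and 0.99^100 = 0.366, so 1 − 0.636 × 0.634 = 59.7%.

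**Chance of no deaths in either arm:** 0.077 × 0.133 = 1.0%, and 0.364 × 0.366 = 13.3%.

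**Check by fitting the model.** Cox fits to 1,500 simulated trials per scenario, censored at 28 days, were non-finite in 20.9% and 60.0%. The simulation standard errors are √(0.199 × 0.801 / 1500) = 1.0 point and √(0.597 × 0.403 / 1500) = 1.3 points, so both agree with the formula.

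**Sensitivity to the assumed plasma rate.** Table 2 prints whole percentages. Halving the control odds exactly gives:
- Scenario 1: odds 0.05/0.95 = 0.0526, halved 0.0263, so pT = 2.56%.
- Scenario 2: odds 0.02/0.98 = 0.0204, halved 0.0102, so pT = 1.01%.

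| Assumption | Scenario 1: deaths; chance of an empty arm | Scenario 2: deaths; chance of an empty arm |
|---|---|---|
| Printed rates | 4.5; 19.9% | 2.0; 59.7% |
| Exact odds ratio 2 | 5.1; 14.6% | 2.0; 59.5% |
| No effect, control rate in both arms | 7.5; 8.2% | 3.0; 44.8% |

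(Last row: 150 × 0.05 = 7.5 and 150 × 0.02 = 3.0.)

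**The other two time-to-event outcomes,** from Table 2 category totals at the printed rates:
- Category 6 or worse (critical care or death). Rates are 10% and 5% in Scenario 1 (5 + 5 = 10 events), and 4% and 2% in Scenario 2 (2 + 2 = 4 events). Chance of an empty arm: 1 − (1 − 0.90^50)(1 − 0.95^100) = 1.1%, and 1 − (1 − 0.96^50)(1 − 0.98^100) = 24.5%.
- Category 4 or worse (hospitalisation or worse). Rates are 30% and 18% (15 + 18 = 33 events), and 12% and 6% (6 + 6 = 12 events). Chance of an empty arm: below 0.5% in both.

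These totals are Day 28 status. People who entered hospital or ICU and recovered before Day 28 would add events. Participants already in hospital at entry, whom inclusion criterion 4 allows, are not new events.

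**The case against.** **Deaths are already covered by the safety analysis.** A death is a serious adverse event under Section 6.7, and Section 3.2 gives proportions with 95% intervals per arm and Fisher's exact test for such events. A reader might infer from the Cox sentence that deaths could go unreported; the safety paragraph shows otherwise. But it commits to no between-arm effect interval and no Fisher test for death alone. Adverse events are also recorded only from first administration, so a death between randomisation and infusion would fall outside it. It does not deliver the promised efficacy estimate.

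**The final SAP is still to come.** True, and it is where the fix belongs. It does not change the fact that a method for death has already been named.

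**The size depends on assumptions.** This stands. The Scenario 1 figure falls from 20% to 15% at an exact odds ratio of 2, and to 8% with no effect. Deaths after Day 28 would add events if counted, since Section 4.9 assesses status at Day 60; but Section 3.1 sets 28 days and no later rate is given.

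**An interval of some kind may survive.** A reader might infer that no interval can be produced at all. Section 3.2 does not specify Wald limits, and a profile-likelihood interval keeps one finite bound when only one arm is empty. What is lost is the finite hazard ratio and the two-sided interval.

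**Critical care already includes death.** As a cut of the ordinal scale, category 6 or worse contains category 7. This is the natural reading, so only a clarifying sentence is needed.

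**Importance.** Time to death is one of several secondary outcomes, and nothing in the documents says that it ranks above the others.

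**Conclusion.** The concern holds for time to death. Under the plan's own Table 2, Cox would give no finite hazard ratio or two-sided interval with probability of about 20% (Scenario 1) or 60% (Scenario 2). Across the assumptions tried, the range is 8% to 20% in Scenario 1 and 45% to 60% in Scenario 2. This rests on 50 and 100 participants, no losses, and deaths counted to Day 28.

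Two wider conclusions are tempting and not supported. One is that Cox is unsuitable for all the time-to-event outcomes: for hospitalisation or worse an empty arm is very unlikely, and for critical care the problem is material only in Scenario 2. The other is that the trial's decision is weakened: the go/no-go rule uses the Mann-Whitney test on the ordinal rating, in which death is simply the worst category. This is a minor point, worth settling because it is easily settled before unblinding.

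**What to change.** In the final SAP, before unblinding:

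1. **Death.** Make the efficacy analysis the number of deaths by randomised arm, an exact confidence interval for the risk difference, and Fisher's exact test. This extends the Fisher comparison already planned for serious adverse events. If a hazard ratio is reported, use Firth-penalised Cox with profile-likelihood limits. If nobody dies, report the counts and the risk-difference interval only.
2. **Critical care.** State that the event is category 6 or worse, which includes death, and that the same sparse-event method applies if either arm has no events.
3. **Hospitalisation or worse.** Keep the Cox model.

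The cost is about one extra sentence in the SAP and, for death, a slightly less familiar effect measure than the hazard ratio. Sample size, visits, data collection and the primary test do not change.

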## **1.5. SARS-CoV-2 testing**

The Laboratorio de Pesquisa em DST e AIDS do IPEC/FIOCRUZ (LAPCLIN/AIDS), Laboratório de Virus Respiratórios e Sarampo (IOC/FIOCRUZ) or the Center for Infection and Immunity (CII) laboratory will conduct both a quantitative PCR assay and serologic assay. No clinical decisions will be made based on these results.

For asymptomatic individuals, PCR testing alone will be used for screening. For symptomatic individuals, two swabs will be collected from each potential participant, one for ID NOW (or comparable rapid antigen test) and one for a PCR-based test. The ID NOW test results are available in minutes and will make recruitment more efficient. In view of the high specificity of the ID NOW test (99.7%) (Dinnes, et al., 2021), if either the ID NOW and/or the PCR test results is positive, the individual will be confirmed as SARS-CoV-2 positive.

PCR testing will be conducted for all participants at screening, days 0, 3, 7, 14 and 28 and the viral load will be estimated. Results from the baseline ID NOW COVID-19 or PCR tests will be reported to subjects as SARS-CoV-2 positive or negative. Subsequent PCR results will not be shared with the subjects or the clinical research team in order to reduce bias.

ID NOW COVID-19 assay performed on the ID NOW Instrument is a rapid molecular in vitro diagnostic test utilizing an isothermal nucleic acid amplification technology intended for the qualitative detection of nucleic acid from the SARS-CoV-2 viral RNA in direct nasal, nasopharyngeal or throat swabs from individuals who are suspected

of COVID-19 by their healthcare provider within the first seven days of the onset of symptoms. ID NOW COVID-19 received Emergency Use Authorization from the US FDA in September 2020.

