#### 2.1.3. Secondary Objectives:

1. To compare the anti-SARS-CoV-2 titers between the recipients of anti-SARS-CoV-2 plasma versus control (albumin 5%) at days 3, 7, 14, 28 and 90
2. To compare the proportion and duration of SARS-CoV-2 PCR positivity (RT-PCR) between the recipients of the anti-SARS-CoV-2 plasma versus control (albumin 5%) at days 0, 3, 7, 14 and 28
3. To compare the levels of SARS-CoV-2 RNA between the recipients of anti-SARS-CoV-2 plasma and control (albumin 5%) at days 0, 3, 7, 14 and 28

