#### **5.2 Virologic measures**

- Rates and duration of SARS-CoV-2 PCR positivity (RT PCR) at days 0, 3, 7, 14 and 28
- Peak quantity levels of SARS-CoV-2 RNA at days 0, 3, 7, 14 and 28
- Culture positivity at baseline and at day 7 in a subset of specimens
- Correlation between viral culture positivity and PCR positivity for SARS-CoV-2

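### The secondary viral RNA and PCR endpoints count the infusion day (Day 0) as an outcome day and include it in peak RNA, and the analysis text does not say how Day 0 or baseline enters the model

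*Combined protocol and SAP*

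**What the plan says.** All references are to the combined protocol and SAP.

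- Section 2.1.3 (and the protocol summary) compares RNA levels between "anti-SARS-CoV-2 plasma and control (albumin 5%) at days 0, 3, 7, 14 and 28". The PCR-positivity objective names the same days.
- Section 3.1 lists "SAR-CoV-2 PCR positivity (Days 0, 3, 7, 14, 28 in addition to baseline" and "SAR-CoV-2 RNA (Days 0, 3, 7, 14, 28 in addition to baseline". Baseline is named separately, so Day 0 reads as an outcome day. The antibody titer endpoint in the same list starts at Day 3.
- Section 5.2 lists "Peak quantity levels of SARS-CoV-2 RNA at days 0, 3, 7, 14 and 28".
- Section 1.5 provides a second pre-treatment value: "PCR testing will be conducted for all participants at screening, days 0, 3, 7, 14 and 28 and the viral load will be estimated".
- Section 3.2 gives the analysis: "Longitudinal data collected over multiple days (e.g., PCR positivity) will be analyzed using generalized linear mixed models", and "Treatment effects on these variables will be estimated with 95% confidence intervals". It names no fixed effects, visits, baseline term or treatment-by-visit term. It leaves the final analysis plan to be settled before unblinding.
- Section 4.3 puts the Day 0 swab and the infusion in the same visit. The swab is item 8 and product administration item 3; the text does not say which happens first.

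**The concern.** On the day of infusion plasma can have changed the nasal swab little or not at all, so a between-arm comparison at Day 0 carries almost no information about treatment. It can do harm in three ways. If a participant's highest RNA is the Day 0 value, that participant's peak cannot show a benefit. If one treatment effect is averaged over all five visits, a visit with no effect pulls the estimate toward zero. If baseline RNA is neither adjusted for nor constrained, between-patient variation that could be removed stays in the error.

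Section 1 gives viral neutralization as the expected mechanism, so nasal RNA is a direct readout of it. Baseline RNA is likely to vary widely, because the population runs from asymptomatic to moderately symptomatic and qualifying swabs may be up to 7 or 10 days old (Section 2.3.1). Randomization is stratified only by steroid use and vaccination (Section 2.3.5), so chance imbalance in baseline RNA is not controlled by design.

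**Working it through.** **The plan's own figure.** The documents give no power, SD, correlation or effect size for RNA or PCR. The only power statement is for the primary go decision: odds ratio 2, 100 v 50, one-sided 0.15, 74% and 80% (Section 3.3, Table 2). Simulating a stratified Mann-Whitney test with two equal strata (8,000 runs) gives 74.8% for Scenario 1 with an exact odds ratio of 2, 74.4% with the printed plasma column, and 81.0% for Scenario 2 either way. The stated power reproduces and is not in question.

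**Inputs below.** From the plan: 100 v 50, five swab days (0, 3, 7, 14, 28), 95% intervals. Assumed: within-patient correlation r of 0.3 to 0.7, unit SD at each visit, an effect constant over Days 3 to 28, two-sided 0.05, no dropout. Two structures are tried: compound symmetry, and first-order autoregressive in visit order. The variance factor for a difference in means is 1/100 + 1/50 = 0.03.

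**1. One treatment effect over all five visits.** Under compound symmetry each visit has weight 1/5, so the expected estimate is 4/5 = 0.80 of the true effect. Under the autoregressive structure, generalized least squares gives Day 0 weight 1/(2 + 3(1 − r)), so the fraction kept is 1 minus that:
- r = 0.3: 1 − 1/4.1 = 0.756
- r = 0.5: 1 − 1/3.5 = 0.714
- r = 0.7: 1 − 1/2.9 = 0.655

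**2. Adjusting the Day 3 to 28 mean for Day 0.** Under compound symmetry the unadjusted variance is (1 + 3r)/4 and the adjusted variance is (1 + 3r)/4 − r².
- r = 0.3: 0.385/0.475 = 0.81
- r = 0.5: 0.375/0.625 = 0.60
- r = 0.7: 0.285/0.775 = 0.37

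Under the autoregressive structure the ratios are 0.97, 0.89 and 0.71. The variance reduction therefore runs from about 3% to 63%.

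**3. Power in one case** (effect 0.4 SD, r = 0.5, compound symmetry):
- Five-visit main effect: 0.32/√(0.03 × 0.60) = 0.32/0.134, power 66.5%
- Days 3 to 28, unadjusted: 0.4/√(0.03 × 0.625) = 0.4/0.137, power 83.2%
- Days 3 to 28, adjusted: 0.4/√(0.03 × 0.375) = 0.4/0.106, power 96.5%

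Under the autoregressive structure at the same r, adjustment moves power only from 89.5% to 92.5%.

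**4. Day 0 kept as a response with a common mean in both arms.** The standard error equals that of adjustment under compound symmetry (0.106 SD at r = 0.5) and is slightly smaller under the autoregressive structure (0.113 v 0.118). There is no dilution.

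**5. Peak RNA.** Simulated log10 RNA, 400,000 trajectories per arm: Day 0 mean 6, SD 1.5, floor 2, compound symmetry, true reduction 0.5 log10 at every post-infusion visit. All of these are assumptions. Mean declines from Day 0 are given for Days 3, 7, 14 and 28.

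| r | Mean decline | Controls peaking on Day 0 | Effect, peak incl. Day 0 | Effect, peak Days 3–28 | Kept |
|---|---|---|---|---|---|
| 0.3 | 0, 1, 2.5, 4 | 42% | 0.266 | 0.508 | 52% |
| 0.3 | 1, 2, 3.5, 4 | 66% | 0.142 | 0.495 | 29% |
| 0.5 | 0.5, 1.5, 3, 4 | 58% | 0.180 | 0.502 | 36% |
| 0.7 | 0, 1, 2.5, 4 | 46% | 0.227 | 0.500 | 45% |
| 0.7 | 1, 2, 3.5, 4 | 79% | 0.079 | 0.490 | 16% |

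**6. Chance imbalance.** The SE of a baseline difference is √0.03 = 0.173 SD. A difference beyond 0.2 SD in either direction (z = 1.155) is expected in about one trial in four.

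**The case against.** A reader might infer that the plan analyses Day 0 as an outcome instead of adjusting for it. The documents do not support that. Section 3.2 names a model class and stops; it neither states nor rules out a baseline term, Section 3.1 mentions baseline separately, and the final plan is still to come. Nor is listing Day 0 as a response an error in itself: with a common baseline mean it costs nothing (step 4). Day-specific contrasts, which fit the day-by-day wording of Section 2.1.3, are not diluted either.

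A reader might also conclude that the right model is worth 1.8 to 2.5 times the sample size. The arithmetic is correct: (1/0.385)/(0.64/0.44) = 1.79 at r = 0.3 and (1/0.375)/(0.64/0.60) = 2.5 at r = 0.5. But it needs a single main effect over all five visits, a constant effect and compound symmetry, none of which is in the plan. Dropping Day 0 supplies a factor of 1.45 to 1.5 of it, which vanishes with day-specific contrasts.

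Three further points stand. PCR positivity is binary, and entry requires a positive swab at screening or a documented positive PCR in the prior week (Section 2.3.1). Day 0 status should therefore be nearly constant, and adjusting for it recovers little. Peak RNA appears only in Section 5.2, with no stated analysis, and some asymptomatic recent contacts may still have rising RNA at entry, which would reduce the share peaking on Day 0. Finally, because Section 4.3 does not order swab and infusion, Day 0 cannot be assumed to be a clean baseline.

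What does not fall away is the peak. The window in Section 5.2, read naturally, includes Day 0, and its dilution does not depend on any unstated model term.

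**Conclusion.** The point holds for the peak measure as written and conditionally for the mixed model.

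- **Peak RNA:** some of any effect is hidden whenever participants peak on Day 0. About 16% to 52% of the post-infusion peak effect is kept under the assumed declining trajectories, in which 42% to 79% of controls peak on Day 0.
- **Mixed model, dilution:** to about 0.66 to 0.80 of the true effect, only if one treatment effect spans all five visits.
- **Mixed model, precision:** a 3% to 63% variance reduction is forgone, only if post-infusion contrasts are unadjusted and Day 0 means are left free. The size depends heavily on the correlation structure.

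The effect sizes, correlations and trajectories are assumptions, since the documents give none. The benefit is mainly for quantitative RNA. Only secondary endpoints are affected; the go decision rests on the severity rating on Day 28 (or the last one evaluated) and is unchanged. The change is worth making because the baseline values are already collected and the final plan is still open.

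**What to change.** In the final SAP, before unblinding:

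1. State whether the Day 0 swab is taken before infusion, and define baseline: Day 0 if it precedes infusion, otherwise the screening PCR.
2. For log10 RNA, estimate treatment effects at Days 3, 7, 14 and 28 by a mixed model adjusted for baseline log10 RNA, or by a treatment-by-visit model with a common baseline mean in the two arms.
3. For PCR positivity, estimate treatment effects at Days 3 to 28 only.
4. Define peak RNA over Days 3 to 28, with baseline RNA as a covariate.
5. Adjust antibody titers for the screening titer.

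The SAP should say that these definitions govern the day lists in Sections 2.1.3, 3.1 and 5.2. The cost is SAP wording; no new data or visits are needed.
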